## 7.5 Expected duration of participant participation

Trial participation for individual participants will last for 24 months.

## 7.6 Removal of participants from therapy or assessments

Everyone conducting or taking part in this trial should follow the PerSEVERE guiding principles [34] for clinical trial research:

1. Everyone running or taking part in the trial should be aware that participants may choose to change, reduce or stop their participation after they agree to join the trial.
2. The nature and extent of participation changes should be the participant's decision to make, within the limits of what is possible for the trial. Their decision should be informed and freely-given.
3. Everyone running or taking part in the trial should be aware that collecting as much as possible of the trial's planned data can help the trial reach a clear and reliable conclusion.
4. Loss of contact between a participant and researchers should not be considered the same as a participant saying that they want to stop the trial participation.
5. The trial data collection should continue until the trial participant explicitly tells researchers that they want it to stop.
6. Data collected for the trial up to the point the trial participant stops providing data should be used in the trial analysis, and kept with the other trial data until the trial is over.
7. Stopping participation early does not affect participants' right to receive the trial-related information later on, if they want to receive it or if it could be important for them to have.

Participants who become pregnant during the course of the trial will be withdrawn from the trial and should contact their GP for further direction regarding the pregnancy, and their managing clinician for advice on managing LS during pregnancy. The occurrence of pregnancy will be captured at site via the trial *Pregnancy Notification Form* on the trial database.

## 7.7 Withdrawal from the trial

Prior to obtaining informed consent, participants will be informed that entry into the trial is entirely voluntary and that their treatment and care will not be compromised by their decision. It will also be explained that they can withdraw at any time.

The trial site staff must inform NCTU of all withdrawals. If site staff are made aware of a participant's withdrawal of consent for any trial activities, the PI or delegate should record this in the electronic case report form (e-CRF) as soon as possible (and within 24 hours) to ensure the correct procedures are followed by NCTU and the site team.

Stopping participation early does not affect participants' right to receive trial-related information when it becomes available (should they wish to receive). Participants will be asked their reason(s) for withdrawal but are not obliged to provide these. In the event of participant withdrawal, it will be explained that the data collected from them so far will be retained and will

still be used in the analysis of the trial. The data will not be erased as it should be possible to recreate a participant's participation up to their point of any withdrawal. Participants can withdraw from clinic visits, questionnaires, treatment or from all procedures completely. Different level of withdrawal and data collection according to withdrawal levels are summarised in Table 5.

Table 5. Use of data according to withdrawal type

Withdrawal type	Withdrawal procedure	Use of data
Discontinue from ALL trial procedures and data collection (complete withdrawal)	Site will complete relevant e-CRF and inform NCTU as soon as possible. ALL clinic visits, data collection and treatment will stop from the date of withdrawal onwards. Participants will stop participation in the trial completely and will continue with their routine care, if needed. Results of the trial and updates may be communicated with the participant if they consented and still wish to receive updates.	Any data collected prior to participant withdrawal will be retained and used. Data from the date of withdrawal onwards will not be collected.
Discontinue from trial treatment	Site will complete relevant e-CRF and inform NCTU. Participants will cease the trial treatment and will continue with their routine care, if needed.	Any data collected prior to participant withdrawal will be retained and used. From the date of withdrawal onwards, only following data will be collected: 
 
- Number of flares
 
- Time to first flare
 
- Clinical photographs (if consented), VASS and clinical examination
 
- Development of VIN or vulval SCC
 
- Global clinical severity assessment
 
- Vulval development and scarring (in adolescents and children)
 
- Sexual function (adults only)
 
- Condition specific QoL - CDLQI for children and VQLI for adults
 
- Generic utility instrument (health related) – CHU-9D for children and EQ-5D-5L for adolescents/adults
 
- Adverse events
 
- Resource use
 
- Concomitant medication
 

Discontinue from clinic visits	Site will complete relevant e-CRFs and inform NCTU.	Any data collected prior to participant withdrawal will be retained and used.

	
Any participant that requests to discontinue from clinic visits will be marked on the trial database so that next visits will not be populated. Clinic visits will stop from the date of withdrawal onwards but the data can be collected from medical notes and from the trial questionnaire.
	
From the date of discontinuation onwards only following data will be collected:
 
 
- Number of flares
 
- Time to first flare
 
- Development of VIN or vulval SCC
 
- Sexual function (adults only)
 
- Condition specific QoL - CDLQI for children and VQLI for adults
 
- Generic utility instrument (health related) – CHU-9D for children and EQ-5D-5L for adolescents/adults
 
- Adverse events
 
- Resource use
 
- Acceptability of treatment
 
- Adherence to treatment
 
- Concomitant medication
 


Discontinue follow-up questionnaires
	
Site will complete relevant e-CRFs and inform NCTU. Upon participant request to discontinue from trial questionnaires will be marked as withdrawn from questionnaire collection on the trial database and no further contact will be made with the participant for the purpose of obtaining questionnaire follow-up data. Clinic visits and data collection from medical notes will continue.
	
Any data collected prior to participant withdrawal will be retained and used. From the date of discontinuation onwards only following data will be collected:
 
 
- Number of flares
 
- Time to first flare
 
- Clinical photographs (if consented), VASS and examination
 
- Development of VIN or vulval SCC
 
- Global clinical severity assessment
 
- Vulval development and scarring (in adolescents and children)
 
- Adverse events
 
- Concomitant medication
 

Discontinue from two weekly notifications
	
Site will complete relevant e-CRF and inform NCTU as soon as possible. The trial treatment and ALL follow up data collection, apart from two weekly data collection, will continue
	
Any data collected prior to participant withdrawal will be retained and used. From the date of withdrawal onwards, only following data will be collected:
 
 
- Clinical photographs (if consented), VASS and clinical examination
 
- Development of VIN or vulval SCC
 
- Global clinical severity assessment
 
- Vulval development and scarring (in adolescents and children)
 
- Sexual function (adults only)
 
- Condition specific QoL - CDLQI for children and VQLI for adults
 
- Generic utility instrument (health related) – CHU-9D for children and EQ-5D-5L for adolescents/adults
 
- Adverse events
 
- Resource use
 
- Concomitant medication
 

--	---	--

The site team should make every effort to keep their contact with the trial participants, within the scope of this protocol, to collect as much as possible data that can help to answer the research question.

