3. Assess the safety of using potent and superpotent TCSs in the vulval area over 24 months	Adverse events	For the duration of participation	Participant reported/clinical assessment/medical notes
4. Assess the cost-effectiveness of the two treatment strategies.	Resource use	At 3, 6, 12, 18 and 24 months	Questionnaire Participant reported
5. Understand the acceptability of reactive and proactive long-term treatment strategies and the barriers and facilitators to continuing with prescribed treatment	Adherence to treatment	At 3, 6, 12, 18 and 24 months	Questionnaire Participant reported
	Acceptability of treatment	At 12 24 months	Questionnaire Participant reported
	Barriers and facilitators	At 12 months	Qualitative interviews

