### Treatment acceptability and potential barriers/facilitators to treatment

- Acceptability of treatment strategy at 12 and 24 months using a Likert scale.
- Adherence to treatment at 3, 6, 12, 18 & 24 months.
- Qualitative interview sub-study at 12 months.

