### **7.8 Discontinuation and withdrawal following randomisation**

Participants who withdraw after randomisation will not be replaced. In addition, if any significant new information becomes available regarding the treatment they received in the trial, it may be necessary to contact them in the future.

Participants can also opt to discontinue their allocated intervention or receive an alternative treatment, but still continue in the trial for follow-up measures. A record of participants who do not receive allocated treatment regimen, along with the actual treatment regimen they received and the reason for not receiving the allocated treatment, will be kept for analysis purposes. Participants will be asked to continue to provide follow up data in the event that they wish to withdraw from receiving the trial treatment.

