### 10.8 Definition of populations analysed

For the primary analysis, all randomised participants who receive at least one dose of the study medication, will be analysed according to allocated treatment group regardless of adherence to the allocated treatment. This will be supplemented by analysing only the participants who would comply with their allocated intervention. Full definition and cut-off for compliance will be specified in the SAP.

For the secondary outcomes, participants will be analysed according to allocated treatment group regardless of adherence to the allocated treatment.

For the safety outcomes, all randomised participants who receive at least one dose of the study medication will be analysed according to:

- treatment received.

- allocated treatment group regardless of adherence to the allocated treatment.

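### Table 5 stops asking for acceptability once a participant formally discontinues trial treatment, which tilts that outcome towards those who continued; the two-weekly-notifications row also contradicts itself

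*Protocol*

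**What the plan says.** Section 4.4 of the protocol lists two questionnaire outcomes under treatment acceptability: "Acceptability of treatment strategy at 12 and 24 months using a Likert scale" and "Adherence to treatment at 3, 6, 12, 18 & 24 months". They serve secondary objective 5 (section 3.3): "Understand the acceptability of reactive and proactive long-term treatment strategies and the barriers and facilitators to continuing with prescribed treatment".

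Table 5 in section 7.7 sets what is collected after each type of withdrawal. For those who discontinue trial treatment it says "From the date of withdrawal onwards, only following data will be collected" and then lists 12 items. Acceptability and adherence are not among them.

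For those who stop the two-weekly notifications, the procedure column says "The trial treatment and ALL follow up data collection, apart from two weekly data collection, will continue". The data column then gives another closed list, which also lacks both items.

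Section 7.8 says of participants who stop treatment: "Participants will be asked to continue to provide follow up data in the event that they wish to withdraw from receiving the trial treatment". It names no exclusions. It also says that a record of those not receiving the allocated regimen, "along with the actual treatment regimen they received and the reason for not receiving the allocated treatment, will be kept for analysis purposes".

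Section 10.8 sets the analysis rule: "For the secondary outcomes, participants will be analysed according to allocated treatment group regardless of adherence to the allocated treatment".

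**The concern.** Someone who formally gives up a strategy is among the most informative respondents on whether it is acceptable and what hinders staying on it. If Table 5 is followed, that person is still asked about quality of life, sexual function and resource use, but not about acceptability. Whether a rating is missing then plausibly depends on what the rating would have been. If one strategy is abandoned more often than the other, the between-arm comparison is affected as well as the level in each arm. The proactive arm has scheduled twice-weekly applications and the reactive arm has none, so unequal stopping is plausible, although the protocol gives no rates.

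This is a rule about data collection. No analysis plan can recover ratings that were never requested.

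**Working it through.** **Step 1. Compare the rows of Table 5.**

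| Row | Other participant questionnaires kept? | Acceptability listed? | Adherence listed? |
|---|---|---|---|
| Trial treatment | Yes | No | No |
| Clinic visits | Yes | Yes | Yes |
| Follow-up questionnaires | No | No | No |
| Two-weekly notifications | Yes | No | No |

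The follow-up-questionnaires row is coherent: the participant has declined questionnaires. In the treatment and notifications rows the data source does not explain the gap, because other participant questionnaires remain. The clinic-visits row shows that the two items are listed by name where they are meant to be collected. The notifications list (10 items) equals the treatment list (12 items) less the two flare items, so the same gap appears in both.

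**Step 2. Compare with other sections.** Section 7.8 asks treatment discontinuers to keep giving follow-up data. Principle 3 of section 7.6 stresses obtaining as much of the planned data as possible, and principle 5 has collection go on unless the participant explicitly asks for it to end. Objective 5 concerns acceptability and the reasons people do or do not continue. None of these fits a rule that ends the acceptability rating when treatment ends.

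**Step 3. Who is lost.** Table 7 schedules acceptability at months 12 and 24 only.
- Formal stop before month 12: no rating.
- Formal stop between months 12 and 24: the 12-month rating is retained and the 24-month rating is lost.
- Poor adherence without formal discontinuation: both ratings are still requested.

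**Step 4. Illustrate the size.** The protocol gives no figure to reproduce here and no separate discontinuation rate. Section 10.1 pools non-compliance with missing primary outcome data in a 20% allowance. It also defines no proportion rating the strategy acceptable, so the Likert item is treated as yes/no for illustration. Assumptions: a share d = 5% to 20% stops before the rating; 85% of continuers and A = 30% to 60% of stoppers find the strategy acceptable.

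- Reported: 85%, whatever d is.
- All randomised: (1 - d) × 85% + d × A.
- Overstatement: d × (85% - A).

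| d | All randomised, A = 30% | Overstatement (points) | All randomised, A = 60% | Overstatement (points) |
|---|---|---|---|---|
| 5% | 82.25% | 2.75 | 83.75% | 1.25 |
| 10% | 79.5% | 5.5 | 82.5% | 2.5 |
| 20% | 74.0% | 11.0 | 80.0% | 5.0 |

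With 400 randomised 1:1, there are 200 per arm, so 5-20% is 10 to 40 participants per arm.

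**Step 5. Between-arm effect.** Suppose continuers rate both strategies equally, and 15% stop in one arm against 5% in the other. With A = 30%, the all-randomised figures are 76.75% and 82.25%, a difference of 5.5 points. With A = 60%, they are 81.25% and 83.75%, a difference of 2.5 points. The collected data would show 0 in both cases. With equal stopping and equal ratings in the two arms, the true difference is also 0 and only the level is biased.

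**The case against.** Several stronger readings are tempting, and the protocol does not support them.

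- *Acceptability is measured only in those who tolerated their strategy.* This goes too far. Table 5 applies to formal discontinuation, and Step 3 shows who is still rated.
- *The adherence gap damages the complier average causal effect analysis.* This is not shown. Section 7.8 records the regimen received and the reason, so a formal discontinuer can be classed as a non-complier from the stop date. That analysis is supplementary and its compliance cut-off is left to the SAP. Not asking about adherence to a regimen already stopped is defensible.
- *Section 10.8 is contradicted.* It fixes how participants are grouped for analysis. It does not promise that every item is collected after treatment stops.
- *The notifications row produces the same selection.* Those participants remain on treatment, and nothing links declining reminders to disliking the strategy. It is a separate drafting contradiction.

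It can also be said that objective 5 does not rest on the rating alone. Reasons for withdrawal are asked for, though answering is optional, reasons for not receiving the allocated regimen are recorded, and interviews follow at 12 months. But the interviews aim for 10-12 participants per group and do not name discontinuation as a sampling criterion, and a stated reason is not a rating that can be compared between arms.

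Finally, given section 7.8, the Table 5 list may simply be incomplete rather than a deliberate exclusion. That is quite possible, but the list is worded as exclusive, and database schedules could be built from it.

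**Conclusion.** The point holds for acceptability. Under Table 5 as written, participants who formally stop their allocated strategy give no rating from that date, which shifts a secondary outcome towards those who continued and conflicts with section 7.8, principles 3 and 5 of section 7.6 and objective 5. The 1 to 11 point range is illustrative: it depends on the assumed stopping rates and on stoppers rating the strategy lower, and it vanishes if they rate it the same as continuers.

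The notifications row is a plain internal contradiction, covering both acceptability and adherence, with no demonstrated bias. For treatment discontinuers the missing adherence item is minor. The treatment-discontinuation row leaves the primary outcome intact, along with scarring, quality of life, adverse events and resource use. The matter is worth correcting but does not threaten the main result.

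**What to change.** In Table 5:
1. Add acceptability of treatment to the treatment-discontinuation row.
2. Add acceptability and adherence to the two-weekly-notifications row, so that its list matches its own procedure text.
3. Reconcile Table 5 with section 7.8, so that both say the same about what is collected after treatment stops.

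Adding adherence to the treatment-discontinuation row is optional. If leaving acceptability out of that row was intended, state why and describe the outcome as applying to participants who had not formally discontinued.

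The cost is three list entries, a consistency edit and the matching database settings. The questionnaires already exist and these participants remain in follow-up. The change has to be made prospectively, because ratings not requested at months 12 and 24 cannot be obtained afterwards.

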### **7.8 Discontinuation and withdrawal following randomisation**

Participants who withdraw after randomisation will not be replaced. In addition, if any significant new information becomes available regarding the treatment they received in the trial, it may be necessary to contact them in the future.

Participants can also opt to discontinue their allocated intervention or receive an alternative treatment, but still continue in the trial for follow-up measures. A record of participants who do not receive allocated treatment regimen, along with the actual treatment regimen they received and the reason for not receiving the allocated treatment, will be kept for analysis purposes. Participants will be asked to continue to provide follow up data in the event that they wish to withdraw from receiving the trial treatment.

### **7.9 Informed consent**

All participants will provide written informed consent. The PIS will be provided to patients in advance to their appointments, where possible, to ensure that they have sufficient time to consider their participation to the trial. At their screening/baseline visit, the Investigator (or a delegate) will explain the details of the trial and answer any questions that the patient may have concerning the trial. During the discussion, if needed, the usual hospital interpreter and translator services will be available to help with the understanding of the trial, discuss the participant information sheets, and consent forms. However, the consent forms and information sheets will not be available printed in other languages. The Informed Consent Form (ICF) will be signed and dated by the participant before they enter the trial and countersigned by the Investigator (or a delegate).

Where the participant is a child, under age 16, an appropriate age range Participant Information Sheet will be provided. Parental or legal guardian consent must be obtained, however, in addition to parent/guardian consent, assent will be obtained for all children. The assent will be formally captured (signed) for those 12 years and older. In the event of any conflict between the parent and child, the child WILL NOT enter the study. Once a participant reaches the age of legal consent, adult PIS and a specific re-consent form will be used to re-consent.

Informed consent will be collected from each participant before they undergo any interventions (including physical examination and history taking) related to the study. One copy of this will be given to the participant, one will be kept by the Investigator (who will then upload the copy on the trial database), and a third will be retained in the patient's hospital records. Completed ICF will be uploaded on the trial database for monitoring purposes.

Any subsequent amendment to the prevailing protocol, which might affect a participation in the trial, continuing consent will be obtained using an amended consent form which will be signed by the participant.

In this trial participants will be followed up for 2 years to assess for scarring. An optional consent will be obtained for longer term outcomes and economic modelling to allow potential future follow

up through efficient means (such as routine data) as part of a separately funded study, e.g. to investigate malignancy rates and other long-term effects in relation to maintenance regimens (separate funding to be sought if appropriate).

## 8 TRIAL TREATMENT AND REGIMEN

Trial participants will be allocated to either 'Proactive' or 'Reactive' treatment arm. In the 'Proactive' arm, participants will be prescribed their TCS by their treating physician twice a week for 24 months, regardless of presence of LS symptoms. In the 'Reactive' arm, participants will be allocated to use their TCS only when LS symptoms (or increase in visual signs) are present (please refer to table below for more details). The choice of TCS will be at the discretion of the treating physician. Repeat prescriptions will be obtained by participants as per the usual care.

*Table 6. Intervention vs comparator group*

Treatment group	Proactive Intervention group	Reactive Comparator group
Treatment name	Superpotent or potent topical corticosteroid	Superpotent or potent topical corticosteroid
Formulation	Cream/ointment	Cream/ointment
Dosage	1 application twice-weekly on two non-consecutive days in the absence of symptoms. If symptoms flare, apply once a day until symptoms resolve.	Only use during flare. Apply once a day until symptoms resolve.
Route of administration	Topical (application of a thin layer on affected area)	Topical (application of a thin layer on affected area)
Sourcing	Provided directly as per usual care	Provided directly as per usual care
Packaging and labelling	Topical steroid will be provided and labelled as per usual care prescription, and as required for each patient	Topical steroid will be provided and labelled as per usual care prescription, and as required for each patient

Topical dosage of TCSs for both trial groups will be recommended in Fingertip Units (FTU) depending upon area affected by LS (typically 0.5-1 FTU). FTU is the amount of topical steroid (ointment or cream) that is applied along an adult's fingertip to the first crease in the finger. One FTU is sufficient to treat an area of skin twice the size of the flat of an adult's hand with the fingers together (i.e. a 'handprint'). FTU is also used to treat an area of skin on a child. Participants in the 'Proactive' arm will use the recommended amount of their TCS twice per week on a scheduled time of the day. Participants in the 'Reactive' arm will use the recommended amount of their TCS but only when required. If participants are identified to have a flare (regardless of their group allocation) they will be instructed to use the recommended amount once a day until their symptoms subside up to one month. The treating physician will advise on the dosage for adults or children.

All participants will have received advice, as part of clinical care, on a good vulval hygiene routine including avoidance of irritants and the use of emollient as a soap substitute and barrier/moisturiser. The choice of emollient will be usual medical practice for that recruiting site. If, in the proactive arm, a participant forgets to apply their treatment, they should use their ointment/cream as soon as they remember it, provided there is a gap of at least 24 hours between the doses.

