Randomisation and blinding	
Eligible patients who consent will be individually allocated in a 1:1 ratio to either proactive or reactive use of TCS. Treatment will be assigned randomly using a minimisation algorithm with a random element, balancing across groups on:
 
 
• recruitment site
 
• age at randomisation 
 
- children – 5 to <12 years
 
- adolescent – 12 to <16 years
 
- adult – 16 to <45 years
 
- perimenopausal - 45 years & above
 
 
 
• time since last flare (<math>\leq 6</math> months, <math>> 6</math> months)
 
• strength of TCS prescribed (potent or superpotent)
 
 
Allocation will be concealed using a web-based algorithm and held on a secure server, accessed via a secure website.
 
It is not possible to blind the participants, but independent examining clinicians will make assessments of disease activity and scarring at 12 and 24 months and will be blinded to treatment allocation.

Outcome measures	
PRIMARY OUTCOME: Number of flares over 12 months. Flare is defined as worsening of symptoms requiring increased application of TCSs.
 
SECONDARY OUTCOMES: Clinical effectiveness
 
 
• Progression of scarring assessed by blinded assessor at 12 and 24 months by comparing post randomisation assessment to baseline photographs (if patients consented), or assessed clinically if consent has not been given for photographs: 
 
- Adults: scarring worsened (yes/no).
 
- Children and adolescents: failure of normal vulval development (clinical assessment) and/or evidence of scarring (yes/no)
 
 
 

 Symptoms of LS in women and girls include (but are not limited to) itching, burning, pain, painful sexual intercourse, pain on defecation.

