## DEFINITIONS

EMIS & SystemOne	Healthcare software, information technology and related services in the UK, electronic healthcare record system.
REF	Method used in pilot phase for data to be analysed rapidly using framework analysis (REF).
QSR NVivo	Qualitative data analysis software.
Flare	Worsening of symptoms requiring increased application of TCSs as reported by participants via two weekly reminders.
Clinical or biopsy confirmed diagnosis of vulval LS	Clinical diagnosis by an expert by findings of typical clinical features on examination, or by findings on histological examination when assessed by a histopathologist. The trial team will collect information at baseline on clinical vs histological diagnosis.
Resolution of LS symptoms	No more itching/discomfort (resolution of symptoms) as well as improvement of visual signs of flare (bruising under the skin, fissures, skin thickening) back to normal.
End of flare	Participant stops using their topical corticosteroids due to resolution of LS symptoms.
Rescue TSC use	Application once daily until symptoms and signs of active LS resolve (typically 7 days).

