### 4.3 Primary endpoint

Number of flares over 12 months. Flare is defined as worsening of symptoms requiring increased application of TCSs as reported by participants via two weekly reminders.

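### The reactive arm's written trigger for treatment includes visual signs, but a counted flare is defined by symptoms alone, so the primary count could be distorted in either direction

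*Protocol*

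**What the plan says.** The protocol describes the start of treatment, the counted event and the end of a flare in several places.

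- **Reactive arm, section 8 text:** "participants will be allocated to use their TCS only when LS symptoms (or increase in visual signs) are present". The sentence then refers the reader to Table 6.
- **Reactive arm, Table 6:** "Only use during flare. Apply once a day until symptoms resolve".
- **Proactive arm, Table 6:** twice-weekly application, and then "If symptoms flare, apply once a day until symptoms resolve".
- **Both arms, section 8 text after Table 6:** participants identified as having a flare, whichever arm they are in, are told the same thing: "they will be instructed to use the recommended amount once a day until their symptoms subside up to one month".
- **Primary endpoint, section 4.3:** "Flare is defined as worsening of symptoms requiring increased application of TCSs as reported by participants via two weekly reminders". The Definitions table and the synopsis also define a flare by worsening symptoms.
- **What a symptom is, synopsis footnote:** "Symptoms of LS in women and girls include (but are not limited to) itching, burning, pain, painful sexual intercourse, pain on defecation".
- **End of a flare, Definitions:** resolution needs relief of symptoms and also "improvement of visual signs of flare (bruising under the skin, fissures, skin thickening) back to normal". The definition of rescue use likewise runs until both symptoms and signs have resolved.

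**The concern.** Visual signs appear in the reactive arm's treatment instruction and in the definition of resolution. They are absent from the definition of a flare and from the proactive arm's step-up.

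Take a participant, or a parent inspecting a young child, who sees new fissures or bruising without symptoms. In the reactive arm the section 8 text permits treatment, but Table 6 permits it only if this is a flare, and by section 4.3 it is not. In the proactive arm no written instruction links the same findings to extra treatment.

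The number of flares over 12 months is the primary outcome, and unblinded participants report it. For children under 12 the prompt goes to the parent or guardian (Table 3), who can see signs but does not feel symptoms. Time to first flare and the primary economic result, cost per flare averted, rest on the same event. If sign-only episodes are handled or reported differently by arm, all three are affected. The cause could not be traced afterwards unless the reason for each course had been recorded.

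**Working it through.** **1. The wording, compared by arm**

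| Question | Reactive | Proactive |
|---|---|---|
| Start of daily TCS, section 8 text before Table 6 | symptoms or increased visual signs | no sign trigger stated |
| Start of daily TCS, Table 6 | flare | symptoms flare |
| Start of daily TCS, section 8 text after Table 6 | flare | flare |
| Counted as a flare (section 4.3, Definitions, synopsis) | symptom worsening needing more TCS | the same |
| Resolution (Definitions) | symptoms and signs | the same |

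The rule common to both arms does not settle the matter. It applies once there is a flare, and a flare is defined by symptoms. No section says whether a course started for signs alone counts.

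**2. The planned sample size, reproduced first**

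Inputs from section 10.1: rates 4 and 3 per year, dispersion k = 0.34, two-sided 5%, 90% power, one year.

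- n per arm = (1.96·√V0 + 1.2816·√V1)² / (ln 0.75)²
- V1 = 1/4 + 1/3 + 2(0.34) = 1.2633
- V0 at the mean rate of 3.5 = 2/3.5 + 0.68 = 1.2514
- n = 159.5, so 160 per arm and 320 in total; 320/0.8 = 400

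The stated figures reproduce. The point is not an arithmetic error.

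**3. Illustration: flares lost from the count**

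Assume that a share s0 of reactive flares and s1 of proactive flares is treated early on signs, goes unreported, and would otherwise have been counted. The documents give neither share.

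- Observed ratio = 3(1 − s1) / [4(1 − s0)]
- Power at 160 per arm = Φ(|ln ratio| / √(V/160) − 1.96), where V = 1/r0 + 1/r1 + 0.68 and r0, r1 are the reduced rates

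| s0 reactive | s1 proactive | Rates | Ratio | Power |
|---|---|---|---|---|
| 0 | 0 | 4.0 v 3.0 | 0.75 | 90% |
| 5% | 0 | 3.8 v 3.0 | 0.79 | 75% |
| 10% | 0 | 3.6 v 3.0 | 0.83 | 53% |
| 10% | 5% | 3.6 v 2.85 | 0.79 | 73% |
| 10% | 10% | 3.6 v 2.7 | 0.75 | 88% |
| 20% | 20% | 3.2 v 2.4 | 0.75 | 87% |

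**4. Illustration: the opposite direction**

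Any TCS use in the reactive arm is an increase in application. If sign-only courses there were reported as flares on top of the planned 4 a year, adding 5% or 10% to that arm alone, the ratio would be 3/(4 × 1.05) = 0.71 or 3/(4 × 1.10) = 0.68.

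In both illustrations the ratio moves because the arms differ.

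**The case against.** The case against has four parts.

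- **The asymmetry rests on one parenthesis.** The sentence defers to Table 6, which confines the reactive arm to flares, and the following text gives one step-up rule for everyone. On this reading the trigger is common to both arms. That is a fair account of what may have been intended, but Table 6 then contradicts the sentence that points to it, and a site has to choose between them.
- **The protocol does not separate signs from flares cleanly.** The Definitions speak of visual signs of a flare, so the section 8 text may only describe how a flare is recognised. If so, the flare definition is the part that is incomplete, and reconciliation is still needed.
- **It is not shown that such courses would go uncounted.** The symptom list is open-ended, reporting is by the participant, and the wording of the fortnightly prompt is not in the protocol. The rescue algorithm in Figure 2 is not visible either. This part stands. A reader might infer that sign-triggered courses are missed and that the rate ratio is therefore biased towards no difference. The documents do not support that as fact, because the same ambiguity could inflate the reactive count.
- **Compliance is left to the SAP.** Section 10.8 says so, and the missing compliance definition is not criticised here.

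**Conclusion.** The inconsistency is real and touches the primary endpoint. The section 8 text, Table 6, the flare definition and the definition of resolution cannot all be applied as written. Read literally, they allow a course of treatment in the reactive arm that is not a counted flare, with no counterpart written for the proactive arm.

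The consequence is a possible distortion whose direction and size are both unknown. It runs towards no difference if sign-only courses go unreported and pre-empt symptomatic flares, and away from it if they are reported as flares. The 0.79–0.83 range assumes that 5% to 10% of flares are lost from the reactive arm and none from the proactive arm; with equal loss the ratio does not move. These figures show how sensitive the comparison is to an arm-specific difference and do not estimate bias. Nor do the documents support a claim that the problem is larger in children.

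The point merits an amendment because an analysis plan could not later recover the reason for a course that was never recorded.

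**What to change.** 1. Reconcile the Definitions, section 4.3, the section 8 text and Table 6 so that the treatment-trigger wording and the flare definition are consistent, and state explicitly any difference between arms. The choice of clinical trigger rests with the investigators.
2. In the existing fortnightly prompt, record for each start of daily TCS whether it was for symptoms, visual signs or both, in both arms.
3. Pre-specify one sensitivity analysis of the primary outcome that counts every daily-TCS course whatever its trigger, using the same negative binomial model.

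The cost is a wording amendment, one added item in a prompt that is already sent, and one extra analysis. The sample size and visit schedule do not change.
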